3.5 Baseline Assessment Procedures

After completing study informed consent, participants will undergo a comprehensive evaluation to assess for inclusion and exclusion criteria. This will include self-reports and clinician assessments as shown in Table 1. The comprehensive exam will also include a history and physical exam by the study PI (pulse oximetry measurements will be a component of the respiratory evaluation) and baseline medication evaluation for potential harmful interactions. Urine pregnancy tests will be completed for every woman of childbearing potential at the initial assessment and prior to each treatment session. Urine drug screens will be completed for all participants at the initial assessment to detect use of recreational psychoactive substances other than nicotine. Saliva cotinine levels will be measured at baseline, prior to each ketamine session and at 3 month follow up to detect smoking over approximately the previous 6 days. An ECG will be performed in participants with QTc interval of 450ms or longer in males or 460ms in females being exclusionary.

3.6 Intervention Visit Procedures

Prior to administration of the study compounds, participants will complete self-report questionnaires and clinical assessments. Motivational enhancement therapy will be provided before and after ketamine administration, where the reduction of cigarettes and the subject's short and long term smoking-related goals will be discussed with the study physician. The study physician will then disinfect the subject's shoulder using an alcohol wipe, and the study physician will then administer the medication by intramuscular administration into the participant's deltoid muscle. Only individuals who are properly licensed will perform the injection of ketamine. Vital signs will be monitored prior to treatment and posttreatment. If during the post-administration observation period, ketamine administration causes an increase in systolic or diastolic blood pressure >30 mm Hg from baseline, or an increase in pulse rate >30 bpm from baseline, the subject will be treated with a standard of care antihypertensive (i.e. clonidine), and repeat vital sign measurements will be taken approximately every 20 minutes until blood pressure and pulse are within 30 points of baseline values. Medications will be stored in a DHEC compliant locked box within a locked room accessible only to study team members. If the subject experiences symptoms of hypertensive emergency, the subject will be treated with standard of care antihypertensive agents and referred for further assessment and treatment. Subjects experiencing serious adverse effects related to study participation will not receive further administration of ketamine and will be withdrawn from the study. After completion of the injection, when participants return to their neurocognitive baseline per clinical

assessment, they will complete assessments of their perceptual experience of the intervention. We will evaluate the effects of the 3 weekly interventions in 2 follow up sessions. Participants will return for followup assessments 4 and 8 weeks following final medication session. Follow-up visits may be conducted by telehealth. If the follow up is done via telehealth, participants will be given their saliva cotinine tests in advance either at an in person visit or by mail and asked to return them by mail.

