3.4 Schedule of Assessments

The instruments to be used are standardized, have good psychometric properties, and are widely used. The schedule of study assessments is provided in **Table 1**.

Page 8 of 22

Table 1: Schedule of Assessments

	Purpose	TIME POINT						
Instrument Name		BL	Tx 1-3	Follow-up				
		(Wk 0)	(Wk 1-3)	(Wk 4, 8)				
Self-Reports and Consents								
Informed Consent	Obtain informed consent	Х						
Demographics Form	Sample characterization	Х						
General Anxiety Disorder (GAD-7)	Self-report of anxiety symptom severity	х	х	Х				
Insomnia Severity Index (ISI)	Measure of insomnia severity	Х	Х	Х				
Mystical Experiences Questionnaire (MEQ)	Measure of perceptual experiences	Х	х	Х				
Five Facets of Mindfulness (FFMQ)	Assess aspects of mindfulness related	Х	Х	Х				
Fagerstrom Test of Nicotine Dependence (FTND)	Measure of nicotine dependence	х	х	Х				
Questionnaire on Smoking Urges (QSU)	Assessment of smoking cravings	х	х	Х				
Wisconsin Smoking Withdrawal Scale 2 (WSWS2)	Measures severity of smoking withdrawal	х	х	Х				
Timeline Follow- Back (TLFB)	Measure of substance use	Х	Х	Х				
Rhode Island Change Assessment (URICA)	Measure of stage of change	х	х	Х				
Beck Depression Inventory (BDI-II)	Self-report of depression symptom severity	X	×	X				
	Clinician Assess	ments						
History and Physical Exam	Eligibility assessment	Х						
Vital Signs Measurement	Obtain readings of blood pressure, pulse, temperature, respirations and pulse oximetry	Х	X*					
Pre-screening Questionnaire	To assess for basic eligibility criteria before completing a full baseline visit.	Х						

Page 9 of 22

Urine Pregnancy Test (female subjects only)	Eligibility assessment	х	Х	
Electrocardiogram (ECG; subjects with cardiac comorbidities or on QTc prolonging medications only)	Assessment of cardiac function	х		
Urine Drug Screen	Assess for use of psychoactive substances	Х		
Salivary cotinine level	Assessment of smoking status	Х	Х	Х

* Vital signs (blood pressure, pulse, respiratory rate, and pulse oximetry) will be obtained pre- and posttreatment. If there is an increase in systolic or diastolic blood pressure >30 mm Hg from baseline, or an increase in pulse rate >30 bpm from baseline, subjects will be treated with standard of care antihypertensive medications (i.e. clonidine) and the measurements will be repeated every 20 minutes until BP and pulse are within 30 points of the baseline values.

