5.2 Inclusion Criteria

A subject may be eligible for enrollment if all the following inclusion criteria apply within the thirty days prior to first experimental session:

- 1. 21 to 65 years old.
- 2. Able to provide informed consent.
- 3. Be a daily cigarette smoker with multiple unsuccessful previous quit attempts, and report a continued desire to quit smoking.
- 4. Agree to abstain from smoking for the ketamine session from 1 hour before ketamine administration
- 5. Agree to refrain from using any psychoactive drugs, including alcoholic beverages, within 24 hours of ketamine administration. Exceptions include caffeine and nicotine.
- 6. Subjects taking other psychotropic medications must be maintained on a stable dose for at least four weeks before study initiation.
- 7. Be healthy as determined by screening for medical problems via a personal interview, a medical questionnaire, a physical examination, an electrocardiogram (ECG) to verify normal QTc intervals.
- Subjects with normal blood pressure not on antihypertensive medications or medication controlled hypertension as defined baseline visit systolic blood pressure (SBP) <140 mmHg or a diastolic blood pressure (DBP) <90 mmHg.

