5.3 Exclusion Criteria

Subjects will be excluded from the study if any of the following criteria apply:

- 1. Women who are pregnant (positive pregnancy test) or nursing, or are not practicing an effective means of birth control which can include oral, implant, intrauterine device, or patch contraceptive methods as well as barrier contraceptive methods, history of surgery such as hysterectomy or tubal ligation, or abstinence
- 2. Subjects who meet DSM-5 criteria for current or history of psychotic spectrum disorders or current depression or bipolar disorder based on clinical interview.
- 3. Subjects meeting DSM-5 criteria for current substance use disorder other than tobacco use disorder.
- 4. Subjects with hypertension as defined by a baseline visit systolic blood pressure (SBP) >140 mmHg or a diastolic blood pressure (DBP) >90 mmHg.
- 5. A history of allergic or other adverse reaction to ketamine (or its excipients).
- 6. Clinically significant physical exam findings or self-reported medical conditions for which a transient increase in blood pressure could be significantly detrimental (e.g. glaucoma, aneurysmal disease, cardiovascular disease, or end-stage renal disease).
- 7. Cardiovascular conditions: uncontrolled hypertension, angina, a clinically significant ECG abnormality (e.g., atrial fibrillation), TIA in the last 6 months, stroke, peripheral or pulmonary vascular disease
- 8. Subjects who live greater than 20 miles from the study site and cannot arrange their own transportation will be excluded from the study.
- 9. Subjects with clinically significant kidney or liver impairment.
- 10. Have any current neurological illnesses including, but not limited to, seizure disorders, frequent migraines or on prophylaxis, multiple sclerosis, movement disorders, history of significant head trauma, or CNS tumor.
- 11. Morbidly obese (BMI >40), or severely underweight as determined by medical examination.

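### Blood pressure is read before each of the three ketamine injections, but no reading is written at which the injection is withheld

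*Combined protocol and SAP*

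**What the plan says.** Section 3.2 plans three weekly intramuscular sessions. Table 1 (3.4) and its footnote take vital signs before and after each one, and 3.6 repeats this: "Vital signs will be monitored prior to treatment and posttreatment". The pressure rules are these.

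- **Entry.** The last item of 5.2 sets the limit "as defined baseline visit systolic blood pressure (SBP) <140 mmHg or a diastolic blood pressure (DBP) <90 mmHg". Exclusion 4 in 5.3 removes "Subjects with hypertension as defined by a baseline visit systolic blood pressure (SBP) >140 mmHg or a diastolic blood pressure (DBP) >90 mmHg". Both name the baseline visit. The lead sentence of 5.2 requires only that "the following inclusion criteria apply within the thirty days prior to first experimental session".
- **Rise.** The Table 1 footnote acts on this condition: "If there is an increase in systolic or diastolic blood pressure >30 mm Hg from baseline". Section 3.6 states the same threshold but ties it to dosing: "If during the post-administration observation period, ketamine administration causes an increase in systolic or diastolic blood pressure >30 mm Hg from baseline". Both prescribe an antihypertensive and repeat readings about every 20 minutes.
- **Absolute values.** Section 11.2 treats and monitors above 180 systolic, above 105 diastolic, or more than 30 mm Hg above baseline.

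Other safeguards carry no dosing-day number. Exclusion 6 covers "Clinically significant physical exam findings or self-reported medical conditions for which a transient increase in blood pressure could be significantly detrimental". Exclusion 7 begins "Cardiovascular conditions: uncontrolled hypertension, angina". A study physician gives the injection and there is a step for symptoms of hypertensive emergency (3.6). Monitoring is continuous until return to baseline (9.0), and the PI can withdraw a participant (9.0, 10.0).

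**The concern.** Section 11.2 names the transient pressure rise as the most significant physical adverse event of ketamine, and the protocol treats a pressure above 140/90 as too high to enter. A reading that could apply the same caution on the day of dosing is already collected three times per participant, but no rule connects it to the decision to inject.

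Pregnancy is handled differently. It is re-tested before each session (3.5), and a pregnancy leads to withdrawal (9.0).

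Two things are at stake. A participant above the entry limit may be dosed or held depending on who is in the room. And the primary outcome counts people who complete the full treatment (6.1), without saying how a dose postponed for pressure is counted.

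**Working it through.** The plan gives no figure to reproduce. The check is a reading of every pressure rule, followed by an example and a test of whether a risk figure could be attached.

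**1. Rules side by side**

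| Rule | Where | Applies when | Action |
|---|---|---|---|
| 140/90 | 5.2 last item; 5.3 item 4 | Baseline visit | Eligibility |
| Rise >30 mm Hg | Table 1 footnote | Pre- and post-treatment readings, on a natural reading | Treat, re-measure |
| Rise >30 mm Hg | 3.6 | After administration | Treat, re-measure |
| >180, >105 or rise >30 | 11.2 | Not limited in time | Treat, monitor |
| Symptoms of hypertensive emergency | 3.6 | On symptoms | Treat, refer |
| Stopping or withdrawal | 3.6, 9.0, 10.0, 11.4 | Serious adverse effect, pregnancy, best interests, distress, illicit ketamine use | No pressure reading given |

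No row withholds or delays an injection on a pre-dose reading.

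**2. Example.** Baseline visit 138/88, pre-dose 160/100.

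- Rise from the baseline visit: 160 − 138 = 22 and 100 − 88 = 12, both under 30.
- Absolute: 160 < 180 and 100 < 105.
- If *baseline* means the same-day pre-dose reading, the rise at that moment is zero by definition.

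No numeric rule is met on either reading. A further diastolic rise of more than 105 − 100 = 5 would require treatment under 11.2 on both. The systolic margin depends on the meaning of baseline: 138 + 30 = 168, so more than 8; or, with a same-day baseline, 180 is reached before 160 + 30 = 190, so more than 20.

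**3. Age of the qualifying reading.** Table 1 puts baseline at week 0 and the third injection at week 3, so about 21 days. The outer edge is 30 days before the first session plus two weekly intervals: 30 + 14 = 44 days.

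**4. Can a risk multiple be stated?** Inputs from 11.2: mean systolic rise 19.6, with ± 12.8 read as an SD. Assumed: normal rises, and intravenous depression data carried over to 0.71 mg/kg intramuscular. The chance of passing the first systolic trigger T from pre-dose pressure p with mean rise m is 1 − Φ((T − p − m)/12.8).

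| Assumption | From 140 | From 160 | Ratio |
|---|---|---|---|
| Baseline visit at 138, T = 168, m = 19.6 | 1 − Φ((28 − 19.6)/12.8) = 0.256 | 1 − Φ((8 − 19.6)/12.8) = 0.818 | 3.2 |
| Same-day baseline, T = 170 and 180, m = 19.6 | 1 − Φ((30 − 19.6)/12.8) = 0.208 | 1 − Φ((20 − 19.6)/12.8) = 0.488 | 2.3 |
| Same-day, m falls 0.5 per mm Hg above 140 (9.6 at 160) | 0.208 | 1 − Φ((20 − 9.6)/12.8) = 0.208 | 1.0 |
| Same-day, m falls 1 per mm Hg (−0.4 at 160) | 0.2083 | 1 − Φ((20 + 0.4)/12.8) = 0.0555 | 0.27 |

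If the rise occurs only in the 29.8% reported in 11.2, both chances in a row are multiplied by 0.298 and the ratio is unchanged. The ratio runs from 3.2 to below 1 on assumptions the documents do not settle, so none of these figures is a finding.

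**The case against.** A reader might infer that the plan permits dosing at 160/100. The documents do not say so, and silence is not permission. Exclusion 7 bars uncontrolled hypertension without tying it to the baseline visit. Clinical assessments precede the injection, a physician gives it, and the PI may end participation when it no longer serves the participant. What is missing is a number, not all control. In a single-site study of 8 people, some would leave it there.

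The Table 1 footnote and 11.2 can also be read to cover pre-dose readings, so a markedly raised pressure would be treated and re-measured. That is fair, and it is why the gap is clearest in the moderate band. But neither says the injection waits for the repeat reading, and 3.6 confines its rule to the period after administration.

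A reader might also infer that dosing at 160 rather than 140 triples the chance of needing treatment, or that 8 mm Hg of systolic headroom is all that remains. Both need *baseline* to mean the baseline visit, and the first also needs a rise independent of starting pressure. The wording of 3.6, about an increase that ketamine causes, fits a same-day baseline at least as well. Nor is 44 days the usual interval; it is the outer edge.

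Finally, 140/90 is an entry criterion, and nothing in the documents supports it specifically as a dosing-day limit. That stands, so the sponsor should be free to justify another value.

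**Conclusion.** The concern holds in this form: pressure is measured before each injection, no pre-dose value withholds the dose, and the decision is left to unaided physician judgement. This rests on the text alone and needs no model. Its extent is three pre-dose readings per participant with no hold value attached, and a numeric entry limit applied once, about 3 weeks before the last injection and at most 44 days before it.

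No fold-increase and no absolute risk is claimed. The documents do not define *baseline*, do not say how the rise varies with starting pressure, and do not say how often participants will arrive above 140/90. Passing a treatment trigger is also not in itself harm. The existing safeguards limit the consequence but do not make decisions consistent. The sponsor should make the change, which is cheap and concerns the risk that 11.2 ranks first.

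**What to change.** 1. **Section 3.6.** Add: *If pre-dose SBP is >140 or DBP is >90, rest the participant and repeat after 20 minutes, up to twice. If either value is still above the limit, do not inject that day and reschedule. Later injections shift so that weekly spacing is kept. If the limit is exceeded again at the rescheduled visit, do not inject; the PI decides on withdrawal and records the reason.* The values are those of exclusion 4; the sponsor may justify another cut-off, but one should be written.
2. **Table 1 footnote.** Limit the >30 mm Hg clonidine rule to post-administration readings, as in 3.6, and define *baseline* there as the same-day pre-dose reading. Otherwise someone at 110 systolic at the baseline visit and 145 pre-dose (+35) could be due clonidine under the footnote and a hold under 3.6.
3. **Section 3.6.** State that no antihypertensive is given to bring a reading under the limit for injection the same day.
4. **Section 6.1.** State that a rescheduled injection counts as received.

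**Cost.** A few sentences, and repeat readings only when the first is high. The frequency of holds is not in the documents. If 5% to 15% of sessions stayed above the limit after rechecks (assumed, independent), 24 × 0.05 = 1.2 to 24 × 0.15 = 3.6 injections would be postponed, and 1 − 0.95³ = 14% to 1 − 0.85³ = 39% of participants (about 1 to 3 of 8) would face at least one hold. Follow-up visits are timed from the final session (3.2), so they move with it. Each participant who misses an injection for this reason lowers completion by 1/8 = 12.5 percentage points.

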8.4 Study Documentation and Data Handling

Any clinical study event that is judged to be an AE will be recorded on the AE form during the course of the study. The PI and/or trained Research Assistant will ensure this information is captured during every study visit. Whenever a study participant has reported an AE, the study coordinator will discuss the event immediately with the PI (if possible while the study participant is there) who will evaluate the event. If the AE is not serious, the information will be recorded, managed medically as appropriate, and the event will be followed until resolution. SAEs will also be recorded on the AE Form, managed medically as appropriate, and the event is followed until resolution. In addition, the PI will review all completed AE forms for determination of SAE. All SAE reports will be sent to the MUSC IRB within 24 hours of learning of event occurrence.

AEs/SAEs will be documented and reported as per IRB requirements. Research staff will identify AEs and obtain all available information to assess severity, seriousness, study relatedness, expectedness, outcome and the need for change or discontinuation in the study intervention. Adverse events will be documented on AE Logs and additional relevant AE information, if available, will be documented in a progress note in the research record as appropriate to allow monitoring and evaluating of the AE. If the AE meets the definition for Serious, appropriate SAE protocol specific reporting forms will be completed and disseminated to the appropriate persons and within the designated timeframes as indicated above. For each AE/SAE recorded, the research staff will follow the AE/SAE until resolution, stabilization or until the participant is no longer in the study. When a reportable SAE is identified, the research assistant will initiate an SAE form, and the following individuals will be notified within 24 hours of the site's initial notification of the SAE:

1. The PI ([name]) will provide oversight, consultation, assessment, and documentation as appropriate of the SAE.

2. The research staff will notify the MUSC IRB, and complete the AE report form in conjunction with the PI. Communication with the MUSC IRB is through email, memos, official IRB forms, and online reporting.

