If complete information is not available when the initial 24-hour SAE report is disseminated, follow-up information will be gathered to enable a complete assessment and outcome of the event. This information may include hospital discharge records, autopsy reports, clinic records, etc. The research staff will attach

Page 15 of 22

copies of source documents to the SAE report for the PI and for forwarding to the sponsor as appropriate. All deaths that occur during the study or 30 days post termination from the study are required to be reported as adverse events even if they are expected or unrelated. Other adverse events are reportable to the MUSC IRB if the AE is unexpected AND related or possibly related AND serious or more prevalent than expected. All three criteria must be met for an AE to be reported to the MUSC IRB. The IRB definition of unexpected is that the AE is not identified in nature, severity or frequency in the current protocol, informed consent, investigator brochure or with other current risk information. The definition of related is that there is a reasonable possibility that the adverse event may have been caused by the drug, device or intervention.

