9.0 PROVISIONS TO MONITOR THE DATA TO ENSURE THE SAFETY OF SUBJECTS

Ongoing Clinical Monitoring: The research team will closely monitor for any increase in substance use or psychiatric distress at every study intervention visit. The PI will be responsible for assessing potential participants for inclusion and exclusion criteria, and for assessing for adverse effects (AE's) throughout the trial. AE's will be collected, documented, and reported. If the AE is not serious, the information will be recorded, managed medically as appropriate, and the event will be followed until resolution. Serious adverse effects (SAE) will also be recorded on the AE Form, managed medically as appropriate, and the event is followed until resolution. In addition, the PI will review all completed AE forms for determination of SAE. All SAE reports will be sent to the MUSC IRB within 24 hours of learning of event occurrence. The PI will be responsible for withdrawal of a study participant if they become pregnant or feel that participation is no longer in a subject's best interests. Mental health symptoms will be monitored using standardized measures at each visit to detect any worsening symptoms. Additionally, participants will be advised to observe any signs of worsening substance use or psychiatric symptoms, and to discuss these with the research team. All participants will be informed at the initial visit that they may terminate participation at any point. If a participant experiences distress or other problems between visits, he or she will be encouraged to contact [name] or his/her outpatient mental health provider. If a participant needs or desires immediate attention, arrangements will be made for an appointment with an experienced mental health provider. The informed consent document will provide direction to contact the study staff during office hours and/or go to the Emergency Room at any time for worsening of symptoms. In addition, participants will have access to urgent care services at MUSC. If any of the research personnel believes that a participant is medically or psychiatrically compromised by participation, the PI will be notified and

Page 16 of 22

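### Section 3.6 takes participants with a related serious adverse effect out of the study as well as off ketamine, and one sentence of 8.4 could let follow-up of that event end there

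*Combined protocol and SAP*

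**What the plan says.** Section 3.6 attaches two consequences to a serious adverse effect related to the study: the participant "will not receive further administration of ketamine and will be withdrawn from the study". The same section schedules two follow-up assessments after the last ketamine session and adds that "Follow-up visits may be conducted by telehealth".

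Three sentences bear on how long an SAE is followed:

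- 8.4, first paragraph: "SAEs will also be recorded on the AE Form, managed medically as appropriate, and the event is followed until resolution".
- 9.0: "Serious adverse effects (SAE) will also be recorded on the AE Form, managed medically as appropriate, and the event is followed until resolution".
- 8.4, second paragraph, covering every recorded event: "the research staff will follow the AE/SAE until resolution, stabilization or until the participant is no longer in the study".

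Other provisions also apply. On adverse event capture, 8.4 says "The PI and/or trained Research Assistant will ensure this information is captured during every study visit". If the first SAE report is incomplete, "follow-up information will be gathered to enable a complete assessment and outcome of the event". The reporting duty also covers "All deaths that occur during the study or 30 days post termination from the study". Section 10.0 offers referrals to people who are withdrawn.

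**The concern.** Stopping a drug and leaving a study are different events, and 3.6 joins them. The people it removes are those whose later course matters most for Specific Aim 2, which covers safety and tolerability as well as efficacy. Adverse events are collected at visits, and 11.1 promises monitoring at each follow-up visit, so losing the visits loses the planned route for observing these participants. Their cotinine and TLFB data, the two secondary outcomes in 6.2, go as well. The loss is selective, because it falls only on people with a related serious event.

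The second problem is the end point for the event itself. Two staff members could each follow a sentence of the protocol faithfully and close the same SAE at different times.

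**Working it through.** There is no plan figure to reproduce. The check compares the text, with simple counts for scale.

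**1. Who is removed.** Section 3.6 removes people with a related serious adverse effect. Section 9.0 uses that term for an SAE, so the group is participants with a related SAE. The two consequences are joined by a plain conjunction, so study exit is additional to stopping ketamine. The clearest case is an event after session 3: no ketamine remains to be withheld, and the only added effect of the clause is to remove follow-up.

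**2. When follow-up of the SAE ends.**

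| Place | Permitted end points |
|---|---|
| 8.4, first paragraph | resolution |
| 9.0 | resolution |
| 8.4, second paragraph | resolution, stabilization, or study exit |

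The first paragraph of 8.4 agrees with 9.0. The conflict therefore lies inside 8.4, in one sentence.

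**3. The two together.** A related SAE leads to study exit (3.6), and study exit is a permitted end of follow-up (8.4, second paragraph). On that route, follow-up can end at withdrawal. On the other two sentences it continues to resolution. No section says which governs.

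**4. What still operates after withdrawal.** The event is recorded, missing report information is gathered, and deaths are reported to 30 days after termination. None of these sets an end point for a non-fatal event in someone already withdrawn.

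**5. Scale.** Inputs: about 8 participants (5.4); 6 visits each, being 1 baseline, 3 treatment and 2 follow-up (3.2, Table 1).

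- Planned follow-up visits: 8 × 2 = 16. One withdrawal removes up to 2, and 2/16 = 12.5%.
- Visits lost if withdrawal follows session s: 6 − (1 + s), which is 4, 3 or 2 for s = 1, 2 or 3. Both follow-ups are lost in each case.
- Table 1 marks 11 assessments at follow-up (10 self-report instruments plus salivary cotinine): 11 × 2 = 22 per person. If cotinine is taken at only one follow-up, as 3.5 can be read, the figure is 22 − 1 = 21.

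**6. Dating follow-up after an early stop.** Sections 3.2 and 3.6 count four and eight weeks from the last ketamine session, and Table 1 places sessions in weeks 1 to 3. For someone who stops after session 1:

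- counted from the last session received: weeks 1 + 4 = 5 and 1 + 8 = 9;
- counted from the planned third session: weeks 3 + 4 = 7 and 3 + 8 = 11;
- by the Table 1 column label taken literally: weeks 4 and 8.

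Any retention rule therefore has to name its starting date.

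**7. Primary outcome (6.1).** Someone who stops before session 3 has not completed treatment, whether or not they remain in follow-up. For an event at or after session 3, 6.1 does not say whether a withdrawn person who received all three injections counts as a completer.

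**The case against.** The best defence is that 3.6 is clear and uncontradicted. Removing people from a small pilot after a related serious event is a choice the investigators may make, and retaining them goes beyond tidying the text. That stands as far as it goes: the 3.6 part is a design choice with a cost, not an error. The conflict over SAE end points is an inconsistency whatever one thinks of 3.6.

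The event-level safeguards are also real. Staff must obtain all available information on each event, including its outcome, and hospital or clinic records can be gathered without a study visit. A reader might infer from 3.6 and the later sentence of 8.4 that the plan has no SAE follow-up after withdrawal. The documents do not support that: two sentences require follow-up to resolution, and the safeguards above remain. The supported claim is narrower: one sentence permits an earlier stop and nothing resolves the difference.

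The size is modest. Table 1 schedules no vital signs, ECG or physical examination at follow-up, and many of the instruments lost concern smoking, mindfulness or stage of change rather than safety. Section 11.2 says that, in the team's clinical experience with ketamine for depression, unarousable sedation and hypoxia have never occurred at these doses. Section 8.1 plans only descriptive statistics to characterize participants, so no planned efficacy estimate can be shown to be biased. These points limit the consequence. They do not remove the selective loss of the visits at which adverse events, GAD-7, BDI-II, cotinine and TLFB are collected.

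**Conclusion.** The point holds as a recommended change rather than a critical flaw. As written, 3.6 ends study participation for anyone with a related SAE, no section retains that person for the two follow-ups, and the later sentence of 8.4 conflicts with its own first paragraph and with 9.0 on when SAE follow-up ends. Each withdrawal costs up to 2 of about 16 follow-up visits (12.5%) and up to 22 assessments (21 on the single-cotinine reading).

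This rests on enrolment of about 8, two follow-ups per person, and reading withdrawal from the study in its ordinary sense. The size is per withdrawal. The documents give no expected number, so no overall loss is estimated.

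A reader might also conclude either that the primary outcome is untouched or that it is distorted. Neither follows in general. Before session 3 the classification is the same either way; at or after session 3 it is undefined in 6.1.

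**What to change.** Leave the rule on stopping ketamine, and the PI's discretion in 10.0, as they are.

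- **3.6:** distinguish discontinuing study treatment from withdrawing from the study. Keep those who stop treatment in the two existing follow-up assessments, by telehealth where suitable, for data collection only, unless the participant withdraws consent or the PI judges it inappropriate. State the date from which those follow-ups are counted.
- **8.4 and 9.0:** reconcile the later sentence of 8.4 with its first paragraph and with 9.0, so that a single SAE follow-up end point applies, including after withdrawal. Which end point is for the investigators to decide.
- **6.1:** a short clause could say how a withdrawn person who received all three injections is counted.

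The cost is a wording amendment, plus up to two extra contacts for each affected person.
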